4.3 Other Efficacy Endpoints

The following additional efficacy endpoints will be used to compare OKZ with placebo:

- Proportion of subjects achieving an ACR20, ACR50, and ACR70 response and remaining on randomized treatment and in the study, assessed at all other applicable time points
- Proportion of subjects with Simplified Disease Activity Index (SDAI) ≤ 3.3 (remission) and remaining on randomized treatment and in the study, assessed at all applicable time points
- Proportion of subjects with CDAI ≤ 2.8 (remission) and remaining on randomized treatment and in the study, assessed at all other applicable time points.
- Proportion of subjects with DAS28 low disease activity (based on DAS28 [CRP] <3.2) and remaining on randomized treatment and in the study, assessed at all other applicable time points

- Proportion of subjects with improvement from baseline in HAQ-DI score ≥ 0.22 and remaining on randomized treatment and in the study, assessed at all applicable time points
- Change from baseline over time in DAS28 (CRP)
- Change from baseline to Weeks 12 and 24 in DAS28 erythrocyte sedimentation rate (ESR)
- Change from baseline to all other applicable time points in the measure of physical ability (HAQ-DI)
- Change from baseline to Weeks 12 and 24 in the scores for the following patient-reported outcome (PRO) measures:
 - Short Form-36 (SF-36) Physical Component Summary (PCS) and Mental Component Summary (MCS) total scores
 - European Quality of Life-5 Dimensions (EQ-5D)
 - Work Productivity Survey-Rheumatoid Arthritis (WPS-RA)
 - Functional Assessment of Chronic Illness Therapy – Fatigue Scale (FACIT-Fatigue)
- Change from baseline to all applicable time points in SDAI and CDAI
- Proportion of subjects with moderate to good responses for EULAR based on DAS28 (CRP) and remaining on randomized treatment and in the study, assessed at all applicable time points, where a moderate response is defined as either DAS28 (CRP) ≤ 5.1 with an improvement from baseline in DAS28 (CRP) > 0.6 and ≤ 1.2 , or DAS28 (CRP) > 3.2 with an improvement from baseline in DAS28 (CRP) > 1.2 , and a good response is defined as DAS28 (CRP) ≤ 3.2 with an improvement from baseline in DAS28 (CRP) > 1.2
- Change from baseline to all time points in the components of the ACR response criteria

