Contraceptive history/status	✓	✓	✓	✓	✓	✓	✓	✓	✓	✓	✓	✓	✓	✓	✓	✓	✓	✓
Concomitant and prior medications/non-drug therapy	✓	✓	✓	✓	✓	✓	✓	✓	✓	✓	✓	✓	✓	✓	✓	✓	✓	✓
Randomization		✓																
Study treatment allocation through IWRS		✓		✓	✓	✓	✓	✓	✓	✓	✓	✓	✓	✓				
Administer study treatment ^g		✓ ^h		✓	✓	✓	✓	✓	✓	✓	✓	✓	✓	✓				

Assessments ^a		Randomized Double-Blind Treatment Period														Safety Follow-Up Period		
Visit	1	2	3	4	5	6	7	8	9	10	11	12	13	14	15/EoT	SFU-1	SFU-2	SFU-3
Week	Screening	0/Baseline	1	2	4	6	8	10	12	14	16	18	20	22	24 (+2 ^b)	26 (+4 ^b)	30 (+8 ^b)	44 (+22 ^b)
Visit Window (days) for all subjects other than those included in the sample-rich PK subpopulation																		
	-28 to -1	±0	±2	±3	±3	±3	±3	±3	±3	±3	±3	±3	±3	±3	±3	±7	±7	±7
Prescribe rescue medication for nonresponders ⁱ										✓								
EFFICACY ASSESSMENTS																		
Patient Global Assessment of Disease Activity (VAS)		✓		✓	✓		✓		✓			✓			✓			
Patient Assessment of Pain (VAS)		✓		✓	✓		✓		✓			✓			✓			
HAQ-DI		✓		✓	✓		✓		✓			✓			✓			
SF-36, EQ-5D, FACIT-Fatigue, and WPS-RA		✓							✓						✓			
Joint counts (Independent Joint Assessment) ^j	✓	✓		✓	✓		✓		✓	✓		✓			✓			
Physician Global Assessment VAS		✓		✓	✓		✓		✓			✓			✓			
CRP	✓ ^k	✓		✓	✓		✓		✓			✓			✓	✓	✓	
ESR		✓							✓						✓			
LABORATORY/SAFETY ASSESSMENTS																		
AEs/SAEs ^l	✓	✓	✓	✓	✓	✓	✓	✓	✓	✓	✓	✓	✓	✓	✓	✓	✓	✓
IGRA	✓													✓				
HIV serology	✓																	
HBsAg, anti-HBs, anti-HBc, HCV Ab	✓																	
Pregnancy test ^m	✓	✓			✓		✓		✓		✓		✓		✓	✓	✓	✓

Assessments ^a		Randomized Double-Blind Treatment Period														Safety Follow-Up Period		
Visit	1	2	3	4	5	6	7	8	9	10	11	12	13	14	15/EoT	SFU-1	SFU-2	SFU-3
Week	Screening	0/Baseline	1	2	4	6	8	10	12	14	16	18	20	22	24 (+2 ^b)	26 (+4 ^b)	30 (+8 ^b)	44 (+22 ^b)
Visit Window (days) for all subjects other than those included in the sample-rich PK subpopulation																		
	-28 to -1	±0	±2	±3	±3	±3	±3	±3	±3	±3	±3	±3	±3	±3	±3	±7	±7	±7
INR, aPTT, fibrinogen ⁿ		✓			✓				✓						✓			✓
Lipid panel (fasting) ^o		✓			✓				✓						✓			✓
CV risk panel ^p		✓			✓				✓						✓			✓
HbA _{1c}	✓																	
Hematology ^q	✓ ^r	✓	✓		✓		✓		✓		✓		✓		✓		✓	✓
Chemistry panel ^s	✓ ^r	✓	✓		✓		✓		✓		✓		✓		✓		✓	✓
RF and anti-CCP	✓														✓			
Urinalysis ^t	✓	✓							✓						✓			✓
ANA and anti dsDNA antibody		✓													✓			✓
PG		✓ ^u																
Serum biomarkers related to targeted pathway		✓			✓				✓						✓			

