5.4.1.2 Randomization (Visit 2, Week 0)

The results of all Screening procedures must be available at or prior to the baseline visit (Visit 2) to determine eligibility for enrollment into the study. The Investigator must evaluate the results of laboratory tests performed at Screening to determine if any laboratory test results are outside the ranges specified in the eligibility criteria and joint counts should be reconfirmed before randomization; no exceptions to these requirements will be allowed.

If a subject meets all study eligibility criteria, the Investigator will randomize the subject via an IWRS; if not, then the subject should be recorded as a screen failure in the IWRS.

Baseline tests and procedures must be performed before administration of the first dose of study treatment.

The following assessments will be performed:

- Review eligibility criteria.
- Perform joint counts (Independent Joint Assessment).
- After confirmation that the subject has met all study entry criteria, randomize the eligible subject via IWRS to 1 of 3 treatment groups.
- Allocate study treatment through IWRS.
- Administer Patient Global Assessment of Disease Activity (VAS) (see Section 7.1.3).
- Administer Patient Assessment of Pain (VAS) (see Section 7.1.4).
- Administer HAQ-DI (see Section 7.1.10.1).
- Administer SF-36, EQ-5D, FACIT-Fatigue, and WPS-RA (see Section 7.1.10).
- Record AEs.
- Administer Physician Global Assessment (VAS, see Section 7.1.5).
- Record details of contraceptive history/status.
- Record concomitant medications and concomitant non-drug therapies.
- Record weight.

- Perform complete physical examination (see Section 7.6.7.1).
- Record vital signs.
 - BP and pulse also need to be reassessed 1 and 2 hours postdose.
- Perform 12-lead ECG.
- Collect samples for international normalized ratio (INR), activated partial thromboplastin time (aPTT), and fibrinogen.
- Measure ESR (see Section 7.6.6.1).
- Collect sample to measure CRP level.
- Collect samples for lipid panel and CV risk panel (see Section 7.6.6.1).
 - Subjects must attend study sites after fasting (water and concomitant medications are permitted) for at least 9 hours for the purpose of conducting the lipid panel assessment.
- Collect samples for chemistry panel, hematology assessments, antinuclear antibodies (ANA), and double-stranded DNA (dsDNA) antibodies.

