5.4.1.8 Visit 9 (Week 12)

The following assessments will be conducted at Visit 9:

- Administer Patient Global Assessment of Disease Activity (VAS).
- Administer Patient Assessment of Pain (VAS).
- Administer HAQ-DI.
- Administer SF-36, EQ-5D, FACIT-Fatigue, and WPS-RA.
- Perform joint counts (Independent Joint Assessment).
- Record AEs and injection site reactions that have occurred since the previous visit.
- Administer Physician Global Assessment (VAS).
- Record details of contraceptive history/status.
- Record concomitant medications and concomitant non-drug therapies.
- Record weight.
- Perform complete physical examination (see Section 7.6.7.1).
- Record vital signs.
- Collect samples for INR, aPTT, and fibrinogen.
- Measure ESR (see Section 7.6.6.1).
- Collect samples to measure CRP level.
- Collect samples for lipid panel and CV risk panel.
 - Subjects must attend study sites after fasting (water and concomitant medications are permitted) for at least 9 hours for the purpose of conducting the lipid panel assessment.
- Collect samples for chemistry panel and hematology assessments.
 - Subjects must attend study sites after fasting (water and concomitant medications are permitted) for at least 9 hours for the purpose of conducting the chemistry panel.
- Collect blood sample for serum biomarkers related to targeted pathway.
- Collect PK sample (see Table 5).

- Collect sample for analysis of ADAs.
- Perform urine pregnancy test for females of childbearing potential only.
- Collect sample for urinalysis.
- Allocate study treatment through IWRS.
- Administer study treatment.
 - If desired, SC injections may be rotated among the thighs and abdomen.
 - All subjects will remain at the study site for 30 minutes after the injection to be assessed for onset of any systemic injection reactions.

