Missing data may also result from missed intermediate visits for subjects who completed the study. For all binary endpoints, missing intermediate responder status will be imputed from the surrounding visits. If the status at visits both before and after the missed visit is classified as responder, the subject will be considered a responder at the missed visit. Otherwise, the subject will be considered a nonresponder. If an assessment for a given binary endpoint at the last visit is missing for a completing subject, data from the 2 previous visits will be used with the same logic for determining the response status. For the ACR20/50/70 endpoints, if only some components of the response criteria are missing but the available components allow classifying the subject as a responder, the responder category will be used. Otherwise, the method based on surrounding visits as described above will be applied. Similarly, for all continuous endpoints, an average of values from the surrounding visits will be imputed for the missing visit.

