The method of handling missing data that considers discontinued subjects as nonresponders or imputes continuous data with baseline values may be regarded as not conservative if the proportion of subjects dropping out is greater in the placebo group than in the OKZ treatment groups. To address a possibility of this scenario, analysis of primary and secondary efficacy endpoints will be repeated using all collected data (including data post premature study treatment discontinuation) but with missing data after study withdrawal imputed under the following assumptions. Missing post-study withdrawal data for subjects discontinuing from the placebo group will be imputed under the assumption of the Missing-at-Random (MAR) mechanism, where these discontinued subjects are assumed to have post withdrawal values in line with similar placebo subjects who remained in the study, taking into account their values observed prior to discontinuation. For subjects discontinuing from the OKZ treatment groups, missing post withdrawal data will be imputed from the same MAR-based imputation model estimated from the placebo subjects, assuming that after discontinuation, the OKZ subjects will drift towards the mean response of the placebo group. This approach is likely to result in more favorable imputations for the placebo group compared with the nonresponder/return to baseline assumption, while for the OKZ treatment groups, it will not assume a treatment effect beyond the study effect and the effect of the background MTX therapy. This approach will be more conservative compared to the primary analysis if the proportion of subjects discontinuing from the study is greater in the placebo group than in the OKZ treatment groups.

This approach will be implemented with MI using 2 steps. First, intermediate missing data of each continuous parameter will be multiply imputed under the MAR assumption within each treatment group using a multivariate normal imputation model and the Markov chain Monte Carlo (MCMC) method. Second, intermediate missing data imputed in this way will then be used together with observed data for the estimation of the MAR-based model from the placebo group, which will be done using sequential regression imputation models applied to each continuous parameter (Ratitch et al, 2013). The MAR-based placebo imputation model for each parameter will be estimated based on data from placebo subjects and will

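### Averaging the surrounding visits fills a missed Week 12 value with the mean of predose baseline and Week 24 for endpoints measured only at Weeks 0, 12 and 24, so the filled change is half the Week 24 change

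*Combined protocol and SAP*

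**What the plan says.** Section 9.4.8 sends all secondary and other efficacy endpoints to Section 9.4.9.1 for missing data. Under the intermediate-missing-data heading there, the plan notes: "Missing data may also result from missed intermediate visits for subjects who completed the study". It then gives the rule for these gaps: "for all continuous endpoints, an average of values from the surrounding visits will be imputed for the missing visit". The text does not define surrounding visits, and it makes no exception for baseline or for scales measured rarely.

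Section 4.3 lists among the other endpoints: "Change from baseline to Weeks 12 and 24 in the scores for the following patient-reported outcome (PRO) measures". In Table 1 and Table 2 the row "SF-36, EQ-5D, FACIT-Fatigue, and WPS-RA" is ticked only at Weeks 0, 12 and 24, which agrees with the visit lists in Sections 5.4.1.2, 5.4.1.8 and 5.4.2. ESR is ticked at the same three visits, so DAS28 (ESR) can be calculated only then. The Week 0 value is untreated, because Section 5.4.1.2 states: "Baseline tests and procedures must be performed before administration of the first dose of study treatment".

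Section 9.4.9.2 describes another treatment of the same kind of gap, in a sensitivity analysis: "intermediate missing data of each continuous parameter will be multiply imputed under the MAR assumption within each treatment group". That analysis is announced for the primary and secondary endpoints only.

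**The concern.** Averaging two neighbours is harmless when both lie close in time and on the same part of the response curve. Here one neighbour precedes any treatment and the other is 12 weeks after the missed visit. The rule amounts to assuming a straight line from the untreated state to Week 24, with Week 12 exactly half-way. A drug whose primary endpoint is set at Week 12 is expected to have done more than half its work by then.

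The fill is also a single value entered as if observed, so the analysis ignores imputation uncertainty. For withdrawals, the same section uses multiple imputation for exactly that reason. At stake are the Week 12 estimates for the quality-of-life, fatigue and work scales and for DAS28 (ESR). Comparing quality of life is a stated secondary objective (Section 3.2), although these endpoints carry no controlled alpha.

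**Working it through.** The plan gives no figure for this rule, so there is none to reproduce. Its stated disjunctive power (100% and 98%, Section 9.1) concerns binary endpoints and does not enter here.

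**Which visits surround Week 12.** The adjacent scheduled visits, Weeks 10 and 14, collect none of these scales, so averaging those visits would give nothing. The nearest visits with a value are Week 0 and Week 24.

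**Filled value.** Imputed W12 = (W0 + W24)/2. Imputed change = (W0 + W24)/2 − W0 = (W24 − W0)/2, which is half the subject's Week 24 change.

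**Share of the true Week 12 change.** Let r = Week 12 change / Week 24 change. The share is 0.5/r. The documents do not give r, so a range is shown. The arm-mean change retained, when a share m of the arm is filled, is 1 − m + m × 0.5/r; m is also an assumption.

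| r | filled / true change | retained, m = 5% | retained, m = 10% | retained, m = 20% |
|---|---|---|---|---|
| 1.0 | 50% | 97.5% | 95.0% | 90.0% |
| 0.9 | 56% | 97.8% | 95.6% | 91.1% |
| 0.8 | 62.5% | 98.1% | 96.3% | 92.5% |
| 0.7 | 71% | 98.6% | 97.1% | 94.3% |

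So each 5% of subjects filled costs the arm mean 2.5% at r = 1.0 and 1.4% at r = 0.7. If response fades after Week 12 (r = 1.25), the share falls to 40%. If Week 12 is exactly half of Week 24 (r = 0.5), the rule is right.

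**Treatment difference.** Assume true Week 12 changes of 10 (olokizumab) and 5 (placebo), r = 1, true difference 5.00:
- 10% filled in each arm: 10 × 0.95 − 5 × 0.95 = 4.75.
- 10% olokizumab, 2% placebo: 10 × 0.95 − 5 × 0.99 = 4.55.
- 2% olokizumab, 10% placebo: 10 × 0.99 − 5 × 0.95 = 5.15.

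**Contrast with HAQ-DI at Week 12.** HAQ-DI is also collected at Weeks 8 and 18, and those are its neighbours. With an illustrative exponential onset, f(t) = 1 − exp(−t/τ) and τ from 3 to 8 weeks (assumed), the filled HAQ-DI change is (f(8) + f(18)) / (2 f(12)), or 97% to 98% of the true change. The same curves give f(24) / (2 f(12)), or 51% to 61%, for the scales measured three times.

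**The case against.** The strongest reply is that little depends on this. The affected endpoints sit outside the gate-keeping sequence of Section 9.4.6. Section 5.4 has the procedures of an omitted visit done at an Unscheduled Visit, and visit windows are ±3 days, so few completers should lack a Week 12 value. With similar missingness across arms, the rule is conservative for olokizumab. All of that stands, and it limits the severity. It does not make the filled value right. Make-up visits also do not cover every gap: Section 7.1.10.5 sets the FACIT-Fatigue total to missing if an item is unscored, and Section 9.4.9.1 speaks only of missed visits.

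A reader might infer more than the documents support:

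- That the Week 12 treatment effect is halved. Only the filled values are; the arm mean loses a few percent.
- That the bias is always toward zero. The 5.15 case above shows otherwise.
- That the confirmatory HAQ-DI comparison is compromised, because Week 18 follows rescue at Week 14. The averaging barely moves HAQ-DI, and Section 9.4 states that data after rescue are used in the main analyses. Barring post-rescue predictors would be a new model, and would leave a rescued subject with only baseline on these scales.
- That Section 9.4.9.2 already provides the better method for these scales. Its wording on each continuous parameter sits inside an analysis of primary and secondary endpoints, so it does not reach them.
- That the rule cannot work at Week 24. The binary rule for a missing last visit uses the two previous visits, and the continuous rule is introduced as similar. The text is ambiguous. If the binary logic carries over, a missing Week 24 score would again be averaged with baseline.

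**Conclusion.** The point holds in a limited form. For SF-36, EQ-5D, WPS-RA, FACIT-Fatigue and DAS28 (ESR) taken as a composite score, the stated rule gives a missed Week 12 value half of that subject's Week 24 change. This follows from the rule and the schedule alone. How far that is from the true Week 12 change depends on r: 50% of it at a plateau, 56% to 71% for r from 0.9 to 0.7. The effect on the arm mean depends on how many values are filled: about 1.4% to 5% at an assumed 5% to 10%. The direction of the effect on the treatment difference depends on how missingness divides between arms. The single fill also ignores imputation uncertainty. No confirmatory conclusion turns on this, and it ranks as a low-cost improvement.

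**What to change.** In Section 9.4.9.1, replace neighbour averaging for continuous endpoints with multiple imputation under missing at random within each treatment group, using all available visits of that parameter, including visits after rescue. This is the first-step method of Section 9.4.9.2. A missed Week 12 value is then predicted from what subjects in the same arm with similar baseline and Week 24 values showed at Week 12, and not from a fixed half-way point.

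The text should also:
- name the four patient-reported scales and DAS28 (ESR) as covered;
- apply the same model to a missing Week 24 value in completers;
- say whether a score missing at an attended visit is handled the same way;
- combine these imputations with the existing return-to-baseline imputation for withdrawals, analyse each completed dataset by ANCOVA, and pool by Rubin's rule.

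The cost is a wording change to protocol Section 9.4.9.1, carried into the SAP before unblinding, and running the imputation for more parameters than now planned. Data collection, sample size and alpha allocation do not change.

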9.4.9.2 Sensitivity Analyses of Efficacy Endpoints

All sensitivity analyses will be performed based on the ITT population. Multiplicity adjustment procedure will not be applied for the sensitivity analyses. Other sensitivity analyses in addition to those described below may be performed and will be specified in the SAP.

Sensitivity to Data Following Premature Discontinuation of Randomized Treatment

Supportive analyses will be performed to assess the effect of standard of care treatment that the subjects may receive after premature discontinuation of randomized treatment while the subjects remain on study and continue to be evaluated.

In this supportive analysis, all binary efficacy endpoints will be defined regardless of adherence to randomized treatment through the time point of interest. Definitions will be based on the criteria of achieving the corresponding clinical response (e.g., ACR20) using all data collected at the time point of interest, i.e., including data collected post premature

discontinuation of randomized treatment. Subjects who discontinue from study overall, will be considered nonresponders at time points after study discontinuation.

For the supportive analysis of continuous endpoints, data collected post premature discontinuation of randomized treatment will be excluded and replaced with values imputed based on the return to baseline approach implemented with MI as described in Section 9.4.9.1.

These supportive analyses will be performed for all efficacy endpoints.

Sensitivity to Missing Data Assumptions

The method of handling missing data that considers discontinued subjects as nonresponders or imputes continuous data with baseline values may be regarded as not conservative if the proportion of subjects dropping out is greater in the placebo group than in the OKZ treatment groups. To address a possibility of this scenario, analysis of primary and secondary efficacy endpoints will be repeated using all collected data (including data post premature study treatment discontinuation) but with missing data after study withdrawal imputed under the following assumptions. Missing post-study withdrawal data for subjects discontinuing from the placebo group will be imputed under the assumption of the Missing-at-Random (MAR) mechanism, where these discontinued subjects are assumed to have post withdrawal values in line with similar placebo subjects who remained in the study, taking into account their values observed prior to discontinuation. For subjects discontinuing from the OKZ treatment groups, missing post withdrawal data will be imputed from the same MAR-based imputation model estimated from the placebo subjects, assuming that after discontinuation, the OKZ subjects will drift towards the mean response of the placebo group. This approach is likely to result in more favorable imputations for the placebo group compared with the nonresponder/return to baseline assumption, while for the OKZ treatment groups, it will not assume a treatment effect beyond the study effect and the effect of the background MTX therapy. This approach will be more conservative compared to the primary analysis if the proportion of subjects discontinuing from the study is greater in the placebo group than in the OKZ treatment groups.

This approach will be implemented with MI using 2 steps. First, intermediate missing data of each continuous parameter will be multiply imputed under the MAR assumption within each treatment group using a multivariate normal imputation model and the Markov chain Monte Carlo (MCMC) method. Second, intermediate missing data imputed in this way will then be used together with observed data for the estimation of the MAR-based model from the placebo group, which will be done using sequential regression imputation models applied to each continuous parameter (Ratitch et al, 2013). The MAR-based placebo imputation model for each parameter will be estimated based on data from placebo subjects and will

include baseline value of the corresponding parameter and all post-baseline values prior to study discontinuation as explanatory variables. Post study discontinuation missing values in all 3 treatment groups will then be imputed from this single placebo imputation model.

Binary endpoints will then be computed from the multiply imputed data regardless of adherence to randomized treatment through the time point of interest based on the criteria of achieving the corresponding clinical response. Multiply imputed datasets will be analyzed using the same methods as in the primary analysis, followed by combining the results using Rubin's rule (Rubin, 1987).

Additionally, for the primary and secondary endpoints that are binary in nature, a tipping point analysis will be performed. First, binary response status at the time point of interest will be computed using all collected data regardless of adherence to randomized treatment through the time point of interest based on the criteria of achieving the corresponding clinical response. For subjects who withdraw from the study overall, all possible combinations of the number of responders and nonresponders in each treatment group will be considered. The results of analysis for all possible combinations will be summarized graphically, depicting a boundary between combinations that result in a statistically significant treatment effect vs not statistically significant. Clinical plausibility of the combinations on the boundary will be discussed in the Clinical Study Report to evaluate robustness of study conclusions to missing data.

For the secondary endpoint that measures physical ability based on the HAQ-DI improvement at Week 12, a continuous responder analysis will also be performed. Subjects will be considered responders at a specified improvement threshold if they experience percent improvement in the HAQ-DI score from baseline to Week 12 that is greater or equal to the specified threshold and if they remain on the randomized treatment and in the study through Week 12. This analysis will be performed for a range of improvement thresholds from 0 to 100% in 5% increments. The results will be summarized using a graph of proportion of responders in each treatment group versus improvement thresholds.

Sensitivity to Data Following Initiation of Rescue Medication

Sensitivity analyses classifying subjects who receive any rescue medication as nonresponders will be performed for binary efficacy endpoints defined at time points from Week 16 to Week 24.

